2. HOW IT WILL BE DONE

The E-PROOF intervention core content is from publicly available, pre-existing educational content provided by the NIA, NCI, American Cancer Society, American College of Sports Medicine (ACSM), and OSUCCC. The dietary core content includes: 1) recommended amount and sources of protein intake; 2) healthy eating as an OCS; 3) protein intake benefits; and 4) importance of maintaining physical function through diet. The resistance training intervention core content includes: 1) recommended frequency and resistance training exercises; 2) resistance training benefits; 3) different muscle groups; and 4) the importance of maintaining physical function through resistance training. Intervention participants will also have the option of attending Zoom®-based social hours (held at 7-8pm EST, 1 day/week, weeks 3, 6, 9) to share their thoughts and experiences with each other. Informed design was used for intervention development by reviewing relevant evidence; replicating prior successful intervention elements from the PI and co-Is and; incorporating feedback from the Cancer and Aging Research Group's patient advocacy group (see Letter of Support).

Randomization and Baseline Assessment: Subjects will be block randomized by the number of physical function limitations measured by the PFSS.⁴⁰ At the in-person visits at baseline and end-of-study, study staff will measure the physical function (SPPB), muscle strength (handgrip, SPPB), height, weight, and waist circumference of all participants (intervention and control). The Research Electronic Data Capture (REDCap) secure platform^{41,42} will be used for baseline questionnaire data collection, which will assess dietary quality (DHQIII), self-reported exercise, HRQoL, self-efficacy, and demographic and clinical information. After data collection, the research assistant will show intervention participants how to access the REDCap-based logs and enter their weekly dietary intake and exercise adherence. At the end of the baseline visit, intervention participants will receive a binder with printed educational materials on increasing dietary protein, healthy eating, and resistance training to preserve or rebuild lean body mass as a reference tool. Resistance bands (three levels of Thera-bands®), and resistance band exercise guidelines (exercises by muscle group, proper form, how to rate difficulty) will be distributed to intervention participants.

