2. DATA ANALYSIS PLAN

Aim 1: The feasibility of implementing a 12-week online diet and resistance training intervention with OCS will be determined by the study accrual rate, retention rate, and adherence rate. The study accrual rate will be calculated by dividing the number of potential participants that passed screening by the total number of participants started in the study after appropriate informed consent procedures. The recruitment goal is set at 70 participants recruited over a 9-month period. Retention rate will be calculated by dividing the total number of participants initiated by total number of participants in the study at baseline and 12 weeks (end-of-study). Retention goal for this trial is 80%. If 80% (56/70) of participants are retained at end-of-study, the retention goal for this trial will be achieved. Previous studies by the study team had similar recruitment and retention rates of older participants.⁷¹⁻⁷³ We are confident in our ability to recruit and retain the study participants necessary to conduct the proposed study. Participants will be determined to be adherent if they attend ≥80% of the intervention sessions (in-person meetings with study staff and online intervention sessions).^{71,74,75} Overall adherence and

retention rates and associated 95% confidence intervals will be reported at baseline, end-of-study, and 3-month follow-up.

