Aim 2: The primary outcome of the SPPB will be assessed at three time points: baseline, end-of-study, and 3-month follow-up. Efficacy will be based on 12 weeks. The SPPB score is a continuous variable, collected as the total score ranging from 0-12. Group differences in SPPB scores over the time will be tested using repeated measures ANOVA (SAS PROC MIXED). Using the planned contrasts command, we will investigate the changes in SPPB scores within each group, and between the intervention and control groups at end-of-study. Descriptive statistics and frequency distributions will be used to characterize the sample. To examine the effect of the intervention on the changes in physical function, a linear mixed effect model will be adopted using SAS PROC MIXED procedure. The intervention group (intervention vs. control) and time points (baseline, end-of-study, 3-month follow-up) serve as the categorical predictors, together with the intervention*time interaction term. A significant intervention*time interaction effect would indicate a differential change pattern over the time between the groups. Using post-hoc contrasts, we will compare group differences in all collected variables at each time point. Using planned contrasts command, we will investigate for each group the change from baseline to end-of-study, from end-of-study to 3-month follow-up, and from baseline to 3-month follow-up to capture the change patterns over the phases and Bonferroni correction will be applied. Preliminary effect sizes will be generated to inform future trials. A Shapiro-Wilk test, skewness, kurtosis, and Q-Q plots will be used to assess normality of survivor baseline and end-of-study outcomes. Based on normality tests, change in participant outcome measures from baseline to end-of-study will be assessed using paired t-tests or Wilcoxon's signed rank tests.⁷⁶ Analysis will be carried out using intent-to-treat (all participants) and modified intent-to-treat (adherent participants only). All quantitative analyses will be performed using SAS version 9.4.

REFERENCES References

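### Aim 2 names no single primary 12-week between-group SPPB contrast, and its model leaves the baseline means free by arm, which costs precision

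*Combined protocol and SAP*

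**What the plan says.** Everything on this point is under Aim 2 in section V.2 (Data Analysis Plan) unless another section is named.

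- SPPB is the primary outcome, measured at baseline, end-of-study and 3-month follow-up, and "Efficacy will be based on 12 weeks".
- With planned contrasts, "we will investigate the changes in SPPB scores within each group, and between the intervention and control groups at end-of-study".
- The model is introduced with the words "To examine the effect of the intervention on the changes in physical function, a linear mixed effect model will be adopted". Group and the three visits "serve as the categorical predictors, together with the intervention*time interaction term". No baseline covariate or baseline constraint is stated, and neither is a covariance structure.
- A significant group-by-time interaction over the three visits is to be read as a differential pattern of change. "Using post-hoc contrasts, we will compare group differences in all collected variables at each time point". Bonferroni-corrected within-group change contrasts and paired t or Wilcoxon signed rank tests follow.
- The intent-to-treat analysis is to cover all participants, and effect sizes are to inform later trials.
- On randomisation, section III.2 says: "Subjects will be block randomized by the number of physical function limitations measured by the PFSS". That factor is not among the model terms.

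**The concern.** The plan fixes the outcome and the visit but not the quantity to be estimated. The stress on changes, and the post-hoc label on visit-by-visit comparisons, point to a difference in change from baseline. The planned-contrast sentence can equally be read as a difference in end-of-study scores. The overall interaction test and the within-group tests stand beside these without any ranking. An analyst could therefore choose after seeing the data, and the two readings can differ a good deal in precision.

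In addition, group, three-level time and their interaction give six free cell means, two of them at baseline. Randomisation makes the two baseline means equal in expectation, so estimating them separately discards information. Either contrast then has a wider interval than the same data allow. That matters with at most 35 per arm, a hypothesis of statistically significant improvement (Specific Aims), and effect sizes intended for planning the next trial.

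**Working it through.** **The plan's own figure.** Section V.1 gives 27 per group for effect size 0.50, one-sided alpha 0.05 and power 0.80. A one-sample or paired t-test reproduces it: n = 27, power 81.2%. A two-group t-test with these inputs needs 51 per group. With 27 per group it has 57% power, and with 35 per group 66%. The stated figure therefore matches a within-group test and does not settle which between-group contrast is meant.

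**Inputs.**
- 35 randomised per arm (section V.1).
- Retention scenario from Aim 1: "If 80% (56/70) of participants are retained at end-of-study". This is taken as 28 per arm with a week-12 SPPB and 7 per arm with baseline only.
- Effect 0.50, one-sided 0.05 (section V.1). The SD to which 0.50 refers is not stated, so both scales are shown.
- Correlation r between baseline and week-12 SPPB: not in the documents. Assumed 0.5, 0.7 and 0.8, with 0.3 and 0.9 as extremes.
- SD 1 at both visits (assumed).

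**Variance of the 12-week group difference** (known covariance, 3-month visit not used):
- Change contrast, free baselines: 2[(1−r²)/28 + (1−r)²/35]
- Score contrast, free baselines: 2[(1−r²)/28 + r²/35]
- Common baseline mean: 2(1−r²)/28

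At r = 0.7:
- Change: 2[0.51/28 + 0.09/35] = 0.0416
- Score: 2[0.51/28 + 0.49/35] = 0.0644
- Common baseline: 2(0.51/28) = 0.0364
- Ratios to common baseline: 1.14 and 1.77

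| | r = 0.5 | r = 0.7 | r = 0.8 |
|---|---|---|---|
| Variance ratio, change / common | 1.267 | 1.141 | 1.089 |
| Variance ratio, score / common | 1.267 | 1.769 | 2.422 |
| 95% half-width (score SDs), change | 0.52 | 0.41 | 0.34 |
| 95% half-width, score | 0.52 | 0.51 | 0.50 |
| 95% half-width, common | 0.46 | 0.38 | 0.32 |
| Power, 0.5 score SD: change | 60% | 78% | 90% |
| Power, 0.5 score SD: score | 60% | 62% | 63% |
| Power, 0.5 score SD: common | 69% | 83% | 92% |
| Power, 0.5 change SD: change | 60% | 59% | 59% |
| Power, 0.5 change SD: common | 69% | 64% | 62% |

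Half-widths are t(0.975, 54) = 2.005 times the standard error. Power uses the noncentral t with 54 degrees of freedom. A generalised least squares calculation on all 70 participants gives the same ratios.

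**Equivalent sample size, change reading:** 35 × (ratio − 1) = 9.3, 4.9 and 3.1 participants per arm.

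**Extremes.** At r = 0.3 the ratios are 1.43 (change) and 1.08 (score). At r = 0.9 they are 1.04 and 4.41. The common-baseline model is the most precise throughout this range.

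**Estimated covariance.** In simulation (10,000 runs per setting, 7 per arm missing week 12 completely at random), power for a 0.5 score SD effect rises from 59.5% to 68.3%, from 76.8% to 81.2%, and from 90.2% to 91.7% on moving from the change contrast to the common baseline. The gain survives estimation.

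**PFSS factor.** This was simulated as a binary stratum split 18/17 in each arm, with an assumed correlation of 0.3 or 0.5 with SPPB at both visits. Adding it to the common-baseline model gains 0.1 to 3.5 power points. Leaving it out keeps the change contrast at a 4.8–4.9% rejection rate against a nominal 5%, and makes the score contrast conservative at 2.8–4.4%.

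**The case against.** **The plan is conventional, valid and a pilot.** It names SPPB, fixes 12 weeks and lists a between-group comparison at end-of-study, so only change versus score is open. On the likelier reading the gain shrinks as r rises: at r = 0.8 the half-width moves only from 0.34 to 0.32, and at r = 0.9 the standard error differs by about 2%. The largest ratios belong to the less likely reading. This all stands as a limit on size. It does not remove the point: neither planned contrast matches the common-baseline model for any r from 0.3 to 0.9, and at r = 0.7 the two readings of one sentence differ by 16 power points (78% against 62%).

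**The common-baseline constraint needs a baseline SPPB unaffected by allocation, and no section says that it is measured before allocation or by blinded staff.** This is a fair caution. Section III.2 does place the log demonstration and binders after baseline data collection. If knowledge of allocation shifted the baseline by some amount, the change contrast would carry all of that shift and the common-baseline contrast only about r times it. Only the score contrast would escape. The risk is thus no argument for keeping the change contrast.

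**Baseline-only records may not survive,** because section IV.4 deletes the surveys of participants who stop. SPPB is a staff-measured performance test, not a survey. If those records were lost even so, the change ratios would be larger (1.33, 1.18 and 1.11 at r = 0.5, 0.7 and 0.8), although the fix would then retain fewer participants.

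**Conclusion.** The concern holds. Aim 2 does not designate one primary 12-week between-group SPPB contrast, and its model estimates a separate baseline mean in each arm. With 80% retention and r of 0.5 to 0.8, the planned analysis has 9% to 27% more variance than the common-baseline version on the change reading, and 27% to 142% more on the score reading. In power for the 0.50 effect, the loss on the change reading is about 9, 5 and 2 to 3 points at r = 0.5, 0.7 and 0.8.

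These sizes rest on an assumed r, equal SDs and dropout completely at random. Blocking on PFSS may reduce baseline imbalance and so the gain. Both planned contrasts are valid under randomisation, so the issue is avoidable imprecision and an analysis choice left open. The missing PFSS term is minor.

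**What to change.** State one primary efficacy contrast: the 12-week group difference in SPPB from the mixed model, with baseline kept as a response, one baseline mean common to both arms, group terms at the post-baseline visits only, and an unstructured covariance. Label the other SPPB comparisons as secondary or exploratory. Because baseline stays on the response side, every randomised participant with a baseline SPPB contributes, in keeping with the intent-to-treat statement. It would help to state as well that SPPB is measured before allocation is known, if that is so.

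As a minor addition, include the PFSS factor and its interaction with time, with its form fixed in advance: the categories used for blocking, stated in the plan, or one linear term if the raw count was used.

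The cost is a few lines of analysis-plan text and PROC MIXED code, with no new data. Adding PFSS uses a few degrees of freedom; even ten extra terms among 56 completers would cost about 0.2 power points.

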Aim 1: Determine the feasibility and acceptability of implementing a 12-week online dietary and resistance training randomized trial with 70 older cancer survivors. This aim will be accomplished by collecting detailed process data, which allows the assessment of accrual, retention, and adherence. Our hypothesis is that we will recruit (within 9 months) 70 OCS, retain $\geq 80\%$ of the sample, and maintain $\geq 80\%$ adherence to the intervention.

Aim 2: Examine the preliminary efficacy of this 12-week online dietary and resistance training intervention with the intervention participants. Registered dietitians and exercise scientists will provide these participants with tailored dietary and resistance training recommendations, counseling, and educational materials. Our hypothesis is that intervention participants will experience statistically significant, clinically meaningful improvements in physical function and associated health outcomes (i.e., muscle strength, dietary quality, HRQoL, self-efficacy,

weight management) after the 12-week dietary and resistance training intervention and at a 3-month post-intervention follow-up.

METHODS

I. STUDY DESIGN

We will examine the feasibility and preliminary efficacy of a 12-week online dietary and resistance training intervention to improve the physical function of OCS through increased protein consumption, healthy eating, and resistance training. In this pilot randomized controlled trial, participants (n=70) will be randomized to one of the two groups: experimental (online counseling, menus, educational materials) and enhanced control (passive educational materials). We will examine the intervention effects on physical function and associated health outcomes during the 12-week period between the experimental and control group.

II. PARTICIPANT SELECTION

1. *ELIGIBILITY CRITERIA*

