1. SAMPLE SIZE AND JUSTIFICATION

A pilot randomized controlled trial with 70 OCS (n=35 for intervention arm; n=35 for control arm) is the most efficient design to accomplish the aims of this pilot study.⁶¹⁻⁶³ For this study, the minimum sample size is calculated using G*Power. Specifying alpha level to be 0.05 (one-sided), expected power to be 0.80, and an expected effect size of 0.50 for the primary outcome (physical function measured by SPPB), the sample size required is 27 per group. Effect size estimates are based on recommendations for clinically meaningful differences for the SPPB^{64,65} and previous pilot randomized controlled trials utilizing the SPBB reporting effect sizes of similar magnitude.^{66,67} Similar designed pilot randomized controlled trials^{38,68-70} used comparable sample sizes to demonstrate acceptability and feasibility.

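### The within-arm 12-week change in SPPB is tested twice under different error rules, and the many between-arm comparisons carry no stated correction

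*Combined protocol and SAP*

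**What the plan says.** All the relevant text is in the Aim 2 paragraph of section V.2, Data Analysis Plan.

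- SPPB is the primary outcome, and efficacy is to be judged at 12 weeks. An early sentence plans SPPB contrasts within each group and between the groups at end-of-study. No correction is mentioned there.
- Between-arm comparisons are then widened: "Using post-hoc contrasts, we will compare group differences in all collected variables at each time point".
- The next sentence plans three changes in each group (baseline to end-of-study, end-of-study to follow-up, baseline to follow-up) and closes "from baseline to 3-month follow-up to capture the change patterns over the phases and Bonferroni correction will be applied". It does not say whether the family is three contrasts (per group) or six (both groups).
- Later, "change in participant outcome measures from baseline to end-of-study will be assessed using paired t-tests" or by signed-rank tests, depending on normality checks. No correction is mentioned.
- Intent-to-treat and adherent-only analyses are both planned, and neither is named as primary.

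The only alpha is in section V.1, Sample Size and Justification: "Specifying alpha level to be 0.05 (one-sided), expected power to be 0.80". Section V.2 gives neither alpha nor sidedness. The Aim 2 hypothesis in the Specific Aims predicts that intervention participants will show "statistically significant, clinically meaningful improvements in physical function and associated health outcomes".

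**The concern.** For SPPB, the baseline-to-12-week change within an arm is both one of the Bonferroni-adjusted contrasts and the subject of the later paired test. A p-value between the corrected and uncorrected thresholds is significant under one planned analysis and not under the other, and the plan does not say which governs. This matters because Aim 2 is worded as a significant improvement in intervention participants, which is that same within-arm change.

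The plan's one multiplicity rule sits on these within-arm contrasts. The larger set, between-arm comparisons of every variable, has no stated rule. Taken as written it also includes baseline, where any difference between randomised arms is due to chance.

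**Working it through.** **Inputs.** One-sided alpha 0.05, power 0.80, effect size 0.50 and 35 per arm (V.1). Retention 80%, or 56/70, which is 28 per arm if losses are equal (V.2, Aim 1). Three contrasts per group and two groups (V.2, Aim 2). Assumptions: the 0.50 is applied as a within-arm standardised change, which V.1 does not say, and the Bonferroni family is 3 or 6.

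**Formula.** One-sided paired t-test power = 1 − F(t(1−α, n−1); n−1, λ), where F is the noncentral t distribution function and λ = d√n.

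**1. The plan's own figure.** V.1 states that "the sample size required is 27 per group". With n = 27, λ = 0.50 × √27 = 2.598, the critical t is 1.706 and power is 0.812. With n = 26, power is 0.798. So 27 reproduces exactly as an uncorrected, one-sided paired test. Two independent means would need 51 per group. A baseline-adjusted between-arm test needs about 49.5 × (1 − r²), which reaches 27 at r ≈ 0.67. A change-score test needs about 49.5 × 2(1 − r), which reaches 27 at r ≈ 0.73. No test or correlation is named, so the paired match shows what the number corresponds to, not what was intended.

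**2. Thresholds for the same change.** Paired test: 0.05. Contrast: 0.05/3 = 0.0167 or 0.05/6 = 0.0083.

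**3. Power at d = 0.50, one-sided.**

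| n per arm | λ | Uncorrected | Family of 3 | Family of 6 |
|---|---|---|---|---|
| 28 | 2.646 | 0.825 | 0.658 | 0.544 |
| 35 | 2.958 | 0.895 | 0.767 | 0.670 |

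For 80% power under Bonferroni, the paired test would need 38 (family of 3) or 45 (family of 6), both above the 35 planned.

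**4. Conflicting verdicts.** If both methods returned the same p-value, the conflict probability is the difference between columns (taken before rounding):
- 28 per arm: 0.167 (family of 3) or 0.280 (family of 6).
- 35 per arm: 0.127 or 0.225.
- No effect: 0.05 − 0.0167 = 0.033, or 0.05 − 0.0083 = 0.042.

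A mixed-model contrast and a paired or signed-rank test will not give identical p-values, so these are guides to size.

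**5. Between-arm family.** The count is an assumption from the outcome list under Data to Be Collected.
- Narrow, at 12 weeks: SPPB 1, grip 1, diet 2, resistance exercise 1, RAND-36 summaries 2, self-efficacy 2, self-regulation 2, eHEALS 1, weight and waist 2 = 14. Adding SPPB, grip and two summaries at follow-up gives 18.
- Wide: both hands and all eight RAND-36 subscales also counted, giving 23 at 12 weeks and 13 at follow-up = 36.

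With independent tests at 0.05 and no true effect, the chance of at least one p < 0.05 is 1 − 0.95^k: 0.51 for k = 14, 0.60 for 18 and 0.84 for 36. The expected number of false positives at k = 36 is 36 × 0.05 = 1.8. With an assumed equal pairwise correlation of 0.5 (one-factor normal model, two-sided tests), the chance is about 0.55 for 36 tests and 0.35 for 14.

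**The case against.** The strongest reply is that the efficacy test is already fixed. SPPB is primary, 12 weeks is the efficacy timepoint, and a between-arm end-of-study contrast is planned outside the Bonferroni clause. That stands. A reader might infer that significance has no fixed meaning anywhere in the plan, or that Bonferroni weakens the main between-arm test. The documents support neither. What remains open is narrower: V.2 does not say that this contrast alone decides efficacy, gives it no alpha or sidedness, and does not rank the two analysis sets.

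The double test is certain only for SPPB. Diet, self-efficacy, self-regulation, eHealth literacy and anthropometry are measured only at baseline and end-of-study, so the paired test is the natural within-arm test for them. For the same reason, comparison at every visit is impossible for most secondary outcomes. That the other comparisons are uncorrected is inferred from silence. The Bonferroni clause attaches by sentence structure to the within-group contrasts, but a wider scope may have been meant. If so, the family is still undefined.

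This is also a pilot seeking preliminary efficacy and effect sizes for later trials. That is a good reason to rely on estimates and intervals, but Aim 2 nevertheless promises statistical significance.

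Two further inferences should be resisted. One is that the uncorrected set lets the Aim 2 claim be met by chance. Aim 2 requires improvement in physical function and in associated outcomes, within the intervention arm, so one chance between-arm result would not satisfy it. If tests are two-sided, the chance of any false positive favouring the intervention is 1 − 0.975^36 = 0.60 even for 36 independent tests. The other is that Bonferroni on the post-programme contrast would let a real loss pass as maintenance. Nowhere do the documents say that a non-significant contrast will be read that way.

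**Conclusion.** The concern holds in a limited form. Followed literally, V.2 gives two decision rules for the within-arm 12-week SPPB change. They would disagree in about 13% to 28% of trials at a true within-arm change of 0.50, and in 3% to 4% with no effect. This rests on the one-sided 0.05 from V.1, on reading 0.50 as a within-arm effect, on 28 to 35 per arm, on a family of 3 or 6, and on both methods giving the same p-value.

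Separately, no correction is stated for a broad between-arm set. Its family-wise error is 0.51 to 0.84 under independence for 14 to 36 tests, and lower with correlated outcomes. The upper figure needs 36 independent tests, which is not realistic for subscales and summaries of one questionnaire. The planned between-arm SPPB contrast at 12 weeks is not itself affected by the Bonferroni clause. The plan should be clarified, but the design is not undermined.

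**What to change.** In section V.2, Aim 2:

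1. Name the already planned 12-week between-arm SPPB contrast, under intent-to-treat, as the single efficacy test. State its alpha and sidedness.
2. Delete the paired or signed-rank test for SPPB, or label it descriptive.
3. State the family for the within-arm SPPB phase contrasts (three or six) and use Holm instead of Bonferroni. Holm gives the same error control and never less power.
4. Drop significance tests between arms at baseline and describe the arms instead.
5. Report all other contrasts as exploratory estimates with 95% confidence intervals, and reword the Aim 2 hypothesis to match.

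The cost is a revision of wording and fewer tests, with no change to visits, data or enrolment. The downside is that secondary outcomes can no longer be called significant.

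### The choice between a paired t-test and a signed-rank test rests on the normality of raw scores, but both tests depend on the within-person changes

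*Combined protocol and SAP*

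**What the plan says.** Section V.2, Aim 2, lists four normality diagnostics: a Shapiro-Wilk test, skewness, kurtosis and Q-Q plots. Their object is the outcome at each of two visits: "Q-Q plots will be used to assess normality of survivor baseline and end-of-study outcomes". The next sentence ties the choice of test to that check. It opens "Based on normality tests, change in participant outcome measures" and goes on to say that "change in participant outcome measures from baseline to end-of-study will be assessed using paired t-tests or Wilcoxon's signed rank tests".

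The plan does not say that the within-person differences are examined. It gives no cut-off, does not say which diagnostic decides, and does not say what happens when one visit passes and the other fails.

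The main SPPB analysis is separate. To examine the effect of the intervention on physical function, "a linear mixed effect model will be adopted using SAS PROC MIXED procedure", with group, time and their interaction. Within-group changes are also tested there, by planned contrasts with a Bonferroni correction. The scale is described thus: "The SPPB score is a continuous variable, collected as the total score ranging from 0-12".

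**The concern.** A paired t-test assumes that the differences are roughly normal. A signed-rank test assumes that they are roughly symmetric. Neither assumes anything about the scores at a single visit, so a check on those scores can mislead in two ways.

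- Raw scores may look non-normal for reasons that cancel in the difference, such as a mix of men and women in a strength measure. The rule then drops a t-test that was sound.
- Raw scores may look normal while the changes are skewed or heavy-tailed. The rule then keeps a t-test where the signed-rank test would serve better.

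Switching tests also changes what is estimated, from a mean change to a rank-based shift. That matters a little in a pilot whose effect sizes are meant to inform later trials. The Aim 2 hypothesis is worded as improvement among intervention participants, so tests of within-person change will be read.

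**Working it through.** **The plan's own figure.** No figure is attached to the normality rule. The nearest is the sample size of 27 per group in V.1, with "expected power to be 0.80, and an expected effect size of 0.50 for the primary outcome" and a one-sided alpha of 0.05. The normal approximation for a paired test is n = ((1.645 + 0.842)/0.50)² = 24.7. The exact noncentral-t calculation gives 26.1, rounded up to 27 (power 0.812). The figure therefore reproduces as a one-sided paired t-test. Two independent groups with the same inputs would need 50-51 per group, which is a separate matter. Correcting the normality rule changes no stated sample size.

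**Why the difference is the relevant quantity.** Let d = (score at 12 weeks) − (score at baseline). The paired t statistic is mean(d) / (SD(d)/√n), and the signed-rank test ranks |d|. Only d enters either one. If a strength score is (mean for that sex) + (person and visit deviation), the sex mean cancels in d. A two-humped raw distribution can then give perfectly normal changes.

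**How often the choice differs.** The documents give no SPPB mean, SD or correlation, so every distribution here is an assumption. The raw-score rule was taken as: use signed-rank if Shapiro-Wilk p < 0.05 at either visit. It was compared with Shapiro-Wilk applied to d.

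| Assumed setting | Raw scores rejected | Differences rejected | Rules disagree |
|---|---|---|---|
| SPPB-like, mean 9.5, SD 2, cap 12, r = 0.7, n = 35 | 98% | 64% | 37% |
| As above, mean 8 | 46% | 50% | 50% |
| Strength, half men and half women (means 36 and 22, SD 5.5, r = 0.8), n = 70 | 37% | 5% | 38% |
| Skewed raw scores, normal change, n = 35 | 84% | 5% | 81% |
| Normal raw scores, skewed change, n = 35 | 9% | 100% | 91% |
| Integer 0-12 scores, mid-scale, high correlation, n = 35 | 32% | 97% | 67% |
| Integer 0-12 scores near the ceiling, high correlation, n = 35 | 99.9% | 99.6% | 0.4% |
| Both visits jointly normal, n = 35 | 10% | 5% | 14% |

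Depending on the assumed shift, disagreement in the first setting runs from 34% to 41%. In the strength mixture at n = 35 it falls to about 20%. The fourth and fifth rows show the two directions of error.

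**How often the conclusion differs (two-sided 5%).** The shifted cases use a change that gives about 75-80% power.

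| Setting | Conclusion differs, no change | Conclusion differs, shifted | Power, raw rule v difference rule |
|---|---|---|---|
| SPPB-like, mean 9.5, n = 35 | 0.25% | 0.95% | 0.738 v 0.744 |
| SPPB-like, mean 8, n = 35 | 0.45% | 1.5% | 0.776 v 0.775 |
| Strength mixture, n = 70 | 0.7% | 2.2% | 0.806 v 0.811 |

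With no true change, the raw-score rule rejected in 4.4% to 5.0% of samples. The largest power gap is 0.744 − 0.738 = 0.006.

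**Where it costs something.** With normal-looking raw scores and heavy-tailed changes (assumed t with 2.5 degrees of freedom), the raw-score rule usually keeps the t-test. At n = 35 its power is 0.63, against 0.76 when the differences are checked: a loss of 0.13. Across the runs the loss was about 11-13 points.

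**The case against.** The strongest reply is that test disagreement is not the same as a changed result. That stands. At 28-35 per arm the paired t-test tolerates moderate non-normality, and in the SPPB-like and strength settings the two rules nearly always reach the same conclusion. A reader might take 35-50% as the share of wrong results, or infer that the true error rate is out of control. The calculations support neither.

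Second, a reader might infer that the trial's main p-value hangs on this check. It does not. The SPPB group comparison and the within-group contrasts come from the mixed model, which the rule does not govern. Only the paired tests beside it are affected.

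Third, the Shapiro-Wilk cut-off is a construction. The plan names four diagnostics and no threshold, and the percentages depend on that construction and on assumed distributions. This also stands, and it is why the range is wide: near the SPPB ceiling the rules can agree almost always. The plan also leaves open whether the paired tests are run per arm or pooled, so n = 70 is only one possible case.

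Fourth, one might add that the plan states no residual check for the mixed model. That is an unstated detail rather than an error, and it adds no weight here.

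What survives is narrower: the plan states a rule, and the rule names the wrong quantity.

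**Conclusion.** The point holds as a correction of wording with a small practical effect. As written, V.2 selects a test of change from the shape of single-visit scores, and this can pick the wrong test in either direction. In the SPPB-like settings with SD 2 and r = 0.7, the choice differs from a check on differences in about 35-50% of samples at 35 per arm. For a two-sex strength measure it differs in about 20% (n = 35) to 38% (n = 70 pooled). Other assumed shapes give anything from 0.4% to 91%.

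In the SPPB-like and strength settings, the significance conclusion changes in about 2% of samples or fewer and type I error stays near 5%. The loss becomes material, at about 11-13 points of power, only where changes are heavy-tailed and raw scores look normal. The documents give no data to say whether that will occur. The documents do not support extending the concern to the mixed-model group-by-time analysis, its contrasts, or the trial's overall error rate. Severity: minor.

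**What to change.** In V.2, Aim 2, make one of two changes before the data are seen:

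- Apply the normality assessment to the within-person change from baseline to end-of-study, instead of to the outcome at each visit. State which diagnostic decides and at what threshold.
- Preferably, name one paired analysis for each outcome in advance and drop the pre-test. This also removes the unstated choice among four diagnostics.

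Either change is one sentence. It needs no new data and leaves the sample size, the mixed model and the conduct of the trial as they are.
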